5.3. Research Setting

The research will take place in a number of settings throughout England, covering the South West, South East, London, the Midlands and the North East. These regions have been selected via a competitive expression of interest process to ensure some generalisability and scalability of results. All participants will be resident in temporary accommodation at the time of their recruitment to the trial, and receiving support from one of the charity partners recruited for the trial. Participants will be surveyed over the phone or online for data collection.

5.4. Masking

- Outcome assessors and data analysts will be masked
- Enumerators employed by IFF Research will be blind to participants'
 assignment when collecting data at baseline, midline and endline. The
 principal investigator will randomly define treatment variables at each
 time period to ensure that data analysts will be blind to treatment
 assignment, with unblinding occurring after the analysis is complete.
- Data cleaning and pseudo-anonymisation will be conducted by a separate analyst of the team in order to further guard against possible bias.

6. TARGET POPULATION

6.1. Eligibility

Inclusion criteria

To be included participants must be 18 years old or older, be living in temporary accommodation and have experience of rough sleeping.

Exclusion criteria

Participants will be excluded if they have received a personalised budget from Greater Change in the past, and if they have £4,000 or more in savings. This limit is set so as not to affect people's benefit eligibility.

Participants can be excluded by charity partners if they believe that there is a substantial risk of harm to the participant if they are assigned to the treatment group. Substantial risks of harm will be judged by the frontline worker, and a log of exclusions will be kept. We expect this to be minimal as the monies will be managed by the caseworker.

6.2. Recruitment

Methods

Participants will be recruited by local charity partners appointed to support this trial, who will check participants' eligibility to participate in the trial. As part of this process, charity partners will collect consent to pass on participants' contact details and refer them to Greater Change. Greater Change will then explain the study to participants and collect consent to participate in the trial. The decision to have Greater Change collect consent was made on the basis that doing so would impose a substantial burden on those charity partners and that Greater Change has a more in-depth and nuanced understanding of the intervention, meaning that they would be better placed to explain the intervention consistently to prospective participants.

Screening

Participants will be screened by charity partners based on the eligibility criteria identified above. Charity partners will be briefed on recruitment and screening processes for the trial by King's College London and Greater Change and provided with a script to refer to during this process.

[figure not shown]
6.3. Enrolment

Participants will be enrolled in the trial if they consent to do so and provide their baseline data to IFF. We anticipate enrollment starting in August 2024 and continuing for 5 months.

6.4. Trial Flow Diagram

7. OUTCOME MEASURES

7.1. Primary Outcome

Definition

Following the above Theory of Change, we are primarily interested in measuring potential changes in participants' housing outcomes. Our primary outcome measure will therefore be the number of days out of the 360 days after they were randomised that a person is in secure accommodation. This main analysis will be conducted after the endline data collection 12 months after randomisation.

For this purpose, we will be assessing participants' housing stability and their perceived housing quality and satisfaction (see Annexes B and C). We deem it necessary to complement participants' housing history with questions regarding other relevant aspects of housing such as 1) affordability, 2) choice, independence, privacy, 3) suitability.

Instruments

Questions concerning participants' housing history have been adapted from the Residential Time Line Follow Back Inventory (Tsemberis, S. et al. (2007; see Annex B). Modifications have been mainly made to simplify and adapt the questions to the UK context. Similarly, minor modifications have been made to the OMRA tool, which includes questions about general satisfaction with housing, affordability, choice, independence, and privacy, and suitability.

When is it measured

Participants' data used in this analysis will be collected at three time points: baseline (prior to randomisation) and endline (12 months after randomisation). We will also collect these measures at 6 months after randomisation, and this will be included in our interim analyses.

 For whom is it measured All participants in the treatment and control groups will be surveyed by IFF.

7.2. Secondary Outcomes

We have four secondary outcome measures. These are financial security, participant wellbeing, life satisfaction, and employment.

Financial Security

Definition

Financial security is the extent to which people are, and feel, secure in their finances, and able to be in control of their own destiny financially.

The intervention provides a form of indirect financial relief to participants living in temporary accommodation. As such, it is anticipated to improve financial security and lessen financial distress.

Instruments

We will measure this using the InCharge Financial Distress/Financial Wellbeing Scale (see Annex D). This measure has been validated both in the general population and participants experiencing financial distress. It is an eight-item scale with questions answered on an 11-point response scale from 0-10. This has been adapted from the standard 1-10 scale normally used for this measure, in order to better align with other questions in the same survey and reduce participant confusion and fatigue.

After the end of the baseline period, partway through the midline follow up collection, it became apparent that one of the eight questions in the survey had been omitted from the baseline surveys, and that the survey had been coded as a 1-10 scale, rather than the intended 0-10 scale. Once this issue was identified, subsequent surveys were amended to include all 8 questions, using a 0-10 scale. However, to ensure a consistent methodological approach across all three timepoints, minimising potential biases arising from differences in survey structure, the following mitigations were put in place:

- Analysis of the measure across all timepoints will include only the original seven questions included in the baseline survey.
- The endline and midline surveys will be analysed on a 1-10 scale to align with the baseline collection, with any 0 ratings re-coded as a rating of 1.
- When is it measured?
 The outcome measure is collected at the three data collection points baseline, midline, and endline.
- For whom is it measured?
 All participants in the treatment and control groups will be surveyed by IFF.

Subjective Wellbeing

Definition

Subjective wellbeing is the general sense that people have that their lives are going well and that they experience positive emotions.

Per the Theory of Change diagram, it is anticipated that increased housing and financial security will also have an effect on participants' general wellbeing.

Instruments

We will measure this using the Short Warwick Edinburgh Mental Wellbeing Scale as presented in Annex E (Stewart-Brown et al., 2009). The Short Warwick Edinburgh Mental Wellbeing scale is a widely used and validated measure for subjective wellbeing, recommended by the What Works Centre for Wellbeing. It is a 7-item scale with a 1-5 response scale (Ng Fat et al., 2017).

When is it measured?

The outcome measure is collected at the three data collection points - baseline, midline, and endline.

For whom is it measured?
 All participants in the treatment and control groups will be surveyed by IFF.

Life Satisfaction

Definition

Life satisfaction refers to the extent to which respondents feel content and fulfilled with their living conditions. As per the Theory of Change diagram, it is suspected that improved housing and financial security will positively impact life satisfaction.

Instruments

This will be assessed through the first and second items (i.e. life satisfaction and worthwhileness) from the ONS-4 personal wellbeing item battery (see Annex E). Responses will be recorded on an 11-point scale from 0-10.

When is it measured?

The outcome measure is collected at the three data collection points - baseline, midline, and endline.

For whom is it measured?
 All participants in the treatment and control groups will be surveyed by IFF.

Employment

Definition

This will focus on participants' employment status, i.e. whether or not they are engaging in paid work, education or training.

Per the Theory of Change diagram, we suspect that recipients of personalised budgets will be more or equally (but no less) likely to secure or maintain employment.

Instruments

This measure consists of questions which gather information about participants' employment status. It has been developed by CHI and IFF for the purpose of this evaluation (see Annex F), to consistently identify employment outcomes in a way that can be fed into the economic evaluation.

When is it measured?

The outcome measure is collected at the three data collection points - baseline, midline, and endline.

For whom is it measured?

All participants in the treatment and control groups will be surveyed by IFF.

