10.3. Primary Analyses

Analytical approach

Our main analytical approach for our primary analysis is regression analysis, which will be conducted on an intention-to-treat, complete cases basis. For our main housing outcomes, housing stability and perceived housing quality and satisfaction, measured via Residential Time Line Follow Back Inventory and the OMRA tool, we will conduct a linear regression, evaluated at the mean. Formally, this will be an autoregressive (AR-1), model, specified as:

$$Y_{ipt} = \alpha + \beta_1 Y_{ip0} + \beta_2 B_i + \beta_3 X_i + \beta_4 P_p + u_i$$

Where:

 Y_{ipt} is the value of the respective outcome measure (housing stability and perceived housing quality and satisfaction), for participant i at time t (endline in the primary analysis), referred by charity partner p.

 α is a regression constant

 Y_{i0} is the baseline value of the outcome for participant i in charity partner p.

 B_i is a binary treatment indicator set to 1 if participants are treated and zero else.

 X_i is a vector of participant demographic characteristics including gender (operationalised as a trinary variable) and age (operationalised as a categorical variable with 7 values including prefer not to say).

 P_p is a vector of charity partner fixed effects, reflecting that charity partner is a stratification variable.

 u_i is an error term.

This analysis will be conducted with two values of the time indicator, at the midline and endline data collection points, in both cases using the baseline data at time 0 as a control. Uncertainty will be reported through confidence intervals at p-values. We will report the binary indicator of whether the treatment effect is statistically significant, as well as present the p-value continuously and the confidence intervals.

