10.4. Secondary analyses

Our secondary analyses consist of the same analytical approach as the primary analysis but with outcome measures replaced with our four secondary outcomes: financial security, subjective wellbeing, life satisfaction and employment.

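### Recoding 0 to 1 does not convert the 0-10 financial items to the 1-10 baseline scale: if answers are proportional, follow-up items score about 0.3 to 0.6 points low in both arms, and midline mixes two formats

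*Protocol*

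**What the plan says.** Protocol section 7.2 (Financial Security) describes the intended instrument: "It is an eight-item scale with questions answered on an 11-point response scale from 0-10". At baseline one item was missing and "the survey had been coded as a 1-10 scale, rather than the intended 0-10 scale". The discovery came late: "partway through the midline follow up collection, it became apparent that one of the eight questions in the survey had been omitted". From then on, "subsequent surveys were amended to include all 8 questions, using a 0-10 scale".

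Two rules are meant to give one consistent method at all three time points and to limit bias from the change in survey structure:

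- Items: "Analysis of the measure across all timepoints will include only the original seven questions included in the baseline survey".
- Scale: both follow-up waves "will be analysed on a 1-10 scale to align with the baseline collection, with any 0 ratings re-coded as a rating of 1".

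Financial security is a secondary outcome, and section 10.4 says: "Our secondary analyses consist of the same analytical approach as the primary analysis". In section 10.3 that approach is a regression at midline and at endline, "in both cases using the baseline data at time 0 as a control". Baseline is thus a covariate with its own coefficient, not part of a change score.

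Three other places depend on how scores compare across waves. Section 10.2 promises the distribution of outcomes at each wave. Section 10.6 fills a missing midline value with the endline value and the reverse. Section 10.9 names last observation carried forward.

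**The concern.** A 1-10 and a 0-10 format that run between the same end labels differ along the whole scale, not only at the bottom label. Changing 0 to 1 makes the lowest code match but leaves the answers between the ends where they were. The rule therefore does not achieve the alignment it is written for.

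Midline has a further problem. Section 7.2 implies that early midline respondents answered the old version and later ones the amended version. The wave would then pool two formats, and the model has no term to separate them. The protocol does not say how midline divides between versions.

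At stake are the reading of baseline-to-follow-up movement, the analyses that carry scores from one wave to another, and some precision at midline and endline.

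**Working it through.** **Inputs.** From section 7.2: baseline 1-10 with seven items; amended survey 0-10 with eight items; recode 0 to 1 with 1-10 unchanged. From section 9: 270 participants after 25% attrition, pre/post correlation 0.6. The protocol gives no item mean, SD or distribution, so those below are assumptions.

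**The plan's own figure.** There is none for the scale shift. The only effect-size figure is the MDES: (1.960 + 0.842) × √(4/270) × √(1 − 0.6²) = 0.2728, which agrees with the stated 0.273.

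**Shift by category.** Let u in [0, 1] be the respondent's position between the end labels. The 1-10 answer is about 1 + 9u and the 0-10 answer about 10u. An answer of k on 1-10 corresponds to y = (k − 1) × 10/9 on 0-10. The recoded score is max(y, 1), and the shift is max(y, 1) − k.

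| 1-10 answer k | 1 | 2 | 3 | 4 | 5 | 6 | 7 | 8 | 9 | 10 |
|---|---|---|---|---|---|---|---|---|---|---|
| Shift | 0 | −0.89 | −0.78 | −0.67 | −0.56 | −0.44 | −0.33 | −0.22 | −0.11 | 0 |

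Only the two ends are aligned.

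**Average shift.** The mean of 10u − (1 + 9u) is E[u] − 1, and the recode adds one point for each zero. The average shift is therefore E[u] − 1 + P(0). With equal-width answer bins:

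- Uniform answers: 0.5 − 1 + 0.091 = −0.41.
- Beta(2,4), mean 3.83 on 1-10: 0.333 − 1 + 0.069 = −0.60.
- Beta(1,3), mean 3.03, piled near the floor: 0.25 − 1 + 0.249 = −0.50.
- Beta(4,2), mean 7.17: 0.667 − 1 + 0.000 = −0.33.

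If respondents instead round to the nearest point, the same four give −0.45, −0.64, −0.61 and −0.33. Over all eleven distributions tried and both answer rules, the range was −0.33 to −0.64 points per item.

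**Linear conversion.** Putting x = 10u into 1 + 0.9x gives 1 + 9u. In the same distributions the remaining average shift was between −0.02 and +0.03 points.

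**Effect on the randomised comparison.** This was simulated with 270 participants, baseline as covariate and 1,500 replicates per setting, under assumed latent parameters. The two settings had moderately low and very low scores.

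- Type I error was 0.043 to 0.051 under every coding, including a midline pooled half and half.
- Endline power at a latent effect of 0.3 SD:

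| Endline score | Moderately low | Very low |
|---|---|---|
| Seven items, 0 recoded to 1 | 0.867 | 0.831 |
| Seven items, native 0-10 | 0.879 | 0.863 |
| Eight items, native 0-10 | 0.883 | 0.871 |

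- Midline power with half the sample on each version and no version term: 0.860 and 0.845 with the recode, 0.876 and 0.866 with 1 + 0.9x.

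The Monte Carlo standard error is about √(0.87 × 0.13/1500) = 0.009 per figure, although codings were compared on the same simulated data. Eight native items gain 0.883 − 0.867 = 0.016 and 0.871 − 0.831 = 0.040 over the planned score. At endline, 1 + 0.9x is a linear change of the seven-item native score and leaves its test statistic unchanged, so conversion alone gives 0.879 and 0.863. The eighth item then adds only 0.004 and 0.008.

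**The case against.** **The response model is untested.** Annex D says that response wording varies by item and refers to a source for the coding. If the wording is tied to particular numbers, people may choose the same number in either format. The recode would then be nearly right, and 1 + 0.9x would be wrong by 1 − 0.1x, for example +0.5 points at an answer of 5. This stands. The shift is conditional on proportional answering, and it is the reason to keep the recode as a sensitivity analysis.

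**No single size can be claimed.** A reader might take about 0.6 points as established. That value needs answers averaging roughly 4 on 1-10, or clustered near the floor with nearest-point answering. The protocol supports neither.

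**The treatment effect is not shown to be biased.** A reader might set the shift against the MDES of 0.273 and infer a threat to the trial's inference. The MDES is a between-arm effect, whereas this shift falls on both arms. Version follows calendar time, and section 5.2 randomises in blocks of four within charity partner, so arms should be balanced over enrolment and due dates. Only a response delay that differs by arm could unbalance version, and nothing in the protocol points to one.

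**Direction is not given.** A reader might infer that financial security will appear to fall. Annex D mixes stress and worry items with satisfaction and confidence items and does not give the direction of each scale. Lower item scores are all that can be said.

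**A common metric has a purpose.** The section 10.3 regression does not need baseline and outcome on one scale, so a reader might conclude that endline should simply move to eight items on 0-10. The substitution in 10.6 and the carried-forward values in 10.9 do need comparable scores, and that change would break them. Keeping the seven common items is sound.

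**Conclusion.** The point holds as a limited defect in a secondary outcome. The recode merges 0 with 1 and does not convert the scale. Under proportional answering, follow-up item scores fall about 0.3 to 0.6 points below their 1-10 equivalent, with the size set by an answer distribution the protocol does not report.

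The distortion reaches the wave-by-wave distributions, baseline values carried forward, and old-version midline values substituted into endline. At midline the pooled formats add noise, worth roughly 1.6 to 2.1 points of power in simulation (0.876 − 0.860 and 0.866 − 0.845) if the wave is split evenly. At endline the avoidable loss from the merged categories and the dropped item is about 1.5 to 4 points under assumed parameters. The randomised contrast is not biased by the shift itself. The change is worth making because it costs little and serves the aim stated in 7.2 better than the present rule.

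**What to change.** Amend section 7.2, using the addendum route in section 13.2 before analysis:

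1. Keep the seven common items as the main score at all waves.
2. Convert each 0-10 answer x by 1 + 0.9x in place of recoding only 0. Leave answers given on the 1-10 version unchanged. Use these scores in the models, the 10.2 tables, the 10.6 substitution and the 10.9 imputation.
3. Add a survey-version indicator to the midline model. It absorbs an average difference between versions under either coding.
4. Report the 0-to-1 recode as a sensitivity analysis, and state that the linear conversion assumes proportional answering.
5. Optionally, report endline on all eight items at native 0-10, adjusted for the seven-item baseline score, as a supplement only.

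The cost is revised wording, a short recode, one extra model term and slightly more reporting. No new participant data are needed, but the version each midline respondent received must be on record, by a flag or by interview date against the date of the change.

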8. DATA COLLECTION

8.1. Data collection methods

IFF Research will be collecting data for the evaluation by carrying out baseline, midline and endline surveys with all participants (both treatment and control).

Our data collection approach is based on the principle of ensuring choice and flexibility to participants. Recognising people's different preferences and needs, data collection will offer multiple channels, reminders and callbacks, multiple points of contact, and incentives for survey completion

The approach to data collection is the product of extensive co-creation between CHI, IFF Research, evaluators, delivery partners, and members of CHI's Lived Experience Panel. Particularly, the insights of the Lived Experience Panel have been instrumental in defining and refining our proposed approach.

Data will be collected primarily through an online (Computer Assisted Web Interview (CAWI)) survey hosted on IFF's Dimensions platform. If participants do not respond to the online survey invitation, then IFF will contact them by phone (Computer Assisted Telephone Interview - CATI) to complete the survey with an experienced telephone interviewer.

To facilitate administration of the surveys, delivery partners (and/or referral organisations they work with) will collect personal data from participants, including contact details. This sample data, including any updates to contact details over the life of the evaluation, will be shared with IFF on a rolling basis. IFF will provide delivery partners with a template outlining the data they need to collect and share.

Table 6: Data collection procedures and assessment timeline

Assessment point/Data Collection	Type of data	Data collection approach	
Contact details	Contact details	Referral organisations to collect this from participants and share with IFF on a rolling basis	
Baseline	Baseline characteristics, Primary and Secondary outcomes (pre-intervention), Demographics	Online (CAWI) / Phone (CATI) survey by IFF Research	
Midline (6 months after randomisation)	Secondary outcomes	Online (CAWI) / Phone (CATI) survey by IFF Research	
Endline (12 months after	Primary and secondary outcome	Online (CAWI) / Phone (CATI) survey by IFF	

randomisation)	Exploratory outcomes	Research
	Exploratory dateomics	

8.2. Retention strategies

We will employ a comprehensive set of strategies for promoting participant engagement and retention in the data collection process incorporated into the research design. These include:

Modes of communication:

- Asking participants for their preferred channel for communication (e.g. email, WhatsApp, SMS) and matching our approach where possible.
- Offering both online and telephone options for completing the survey.
 In particular, the telephone approach will be important in reaching participants who do not respond to the online survey invite.
- Ensuring all communications from IFF explain clearly who we are, are warm in tone, use simple language, and have a clear message/call to action.
- Using a named phone number and/or providing the telephone number we will call from in advance to reduce the risk of participants not picking up unknown or withheld numbers.

Multiple contact details:

- Asking participants for multiple contact details including mobile phone, landline and email.
- Asking participants for the contact details of a trusted relative or friend, who would be able to let us know how to contact the participant if their details have changed.
- Where possible, providing a list of non-responsive participants to support workers/delivery partners to follow up with participants directly to ensure they are clear on who we are and what steps they should take.

Reminders:

 Using reminders to encourage participation, again matched to participants' preferred communication channel where possible.

Call-back options:

- Sending a message/email to the participant before any calls are made to them to explain that we will be calling them in the next few days and what steps they should take.
- Sending a message/email to the participant after a missed call to confirm the call attempt, explain that we will try again in the next few days and what steps they should take.
- Option to book an appointment for a call back at a time that best suits the participant to complete the survey by phone.
- Leaving voicemails for participants to explain who we are and why we
 are calling, and to clearly explain what will happen next (e.g. we will try
 calling again in the next few days).

• Providing participants with more information if they are unsure about taking part in the survey, and offering a call back in a few days.

Incentives

- Providing a £20 voucher incentive per participant at each data collection point (baseline, midline, endline).
- The details of the data collection approach and the use of different retention strategies are described in the diagram.

